5. STUDY I

5.1 Design

A prospective RCT involving patients with diabetes as well as one of the three deformities and an impending ulcer associated with the mentioned deformities. By randomization, patients will be allocated to either conservative treatment or tenotomy performed by needle.

5.2 Patients

Inclusion criteria

- Patients aged 18 years or above
- Type 1 or 2 diabetes
- Hammer, mallet or claw toe deformity
- Impending ulcer associated with above mentioned deformities
- Able to understand written and oral information
- Ability to follow planned visits and treatment
- Able to provide informed consent in Danish and/or English

Exclusion criteria

- Revascularization procedure in the affected limb planned, or undertaken within the 4 weeks prior to screening
- Hammer, mallet and claw toe that are rigid in both MTP, IP joints
- Ulcer associated with hammer, mallet and claw toe deformities
- Toe pressure < 30mmHg
- Prior major amputations on affected or ipsilateral leg
- Other corrective operation is indicated to treat patients foot deformities as deemed by investigator
- Current treatment with cytotoxic drugs or with systemically administered glucocorticoids
- Treatment of foot ulcers with growth factors, stem cells or equivalent preparations within the 8 weeks prior to screening
- Likely inability to comply with the need for planned visits because of planned activity
- Participation in another interventional clinical foot ulcer-healing trial within the 4 weeks prior to screening
- Prior enrolment in this trial
- Judgement by the investigator that the patient does not have the capacity to understand the study procedures or provide written informed consent

Discontinuation of patients

- Patient discontinues assigned treatment for any reason, while not fulfilling one of the studies accepted endpoints
- Participants who withdraw from treatment will be asked to remain in the trial for follow-up, and data will continue to be collected and analyzed.
- Patient incurs a serious adverse event (SAE), defined as death or sepsis related to the study procedure

- Investigator decides to discontinue patient due to health or compliance reasons
- Patient misses 3 consecutive visits
- Patient misses 5 or more visits during the full treatment period

Patients who discontinue the study early will be invited to have a clinical visit before being discontinued.

Patients that are discontinued will revert to their normal treatment plan, and continue in their respective clinics.

Endpoints

- New ulcer incurred
 - When/if new ulcer is incurred pictures will be send to two external evaluators to be confirmed as new ulcer
- Patient reaches 12 month visit without incurring a new ulcer
- Patient incurs minor or major amputation on either treated or nontreated limb
- Patient receives surgical intervention relevant for the study (other than planned in study)

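### Outcome collection to 12 months is not described for patients discontinued for missed visits, by the investigator or for a procedure-related SAE, although the analysis is stated to be intention to treat

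*Combined protocol and SAP*

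**What the plan says.** All of the discontinuation rules are in section 5.2, under Discontinuation of patients. The triggers include "Patient misses 3 consecutive visits", "Patient misses 5 or more visits during the full treatment period" and "Investigator decides to discontinue patient due to health or compliance reasons". A serious adverse event, defined there as death or sepsis related to the study procedure, is another. So is stopping treatment: "Patient discontinues assigned treatment for any reason, while not fulfilling one of the studies accepted endpoints".

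Three sentences then describe what follows.

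- Retention: "Participants who withdraw from treatment will be asked to remain in the trial for follow-up, and data will continue to be collected and analyzed".
- Last contact: "Patients who discontinue the study early will be invited to have a clinical visit before being discontinued".
- Afterwards: "Patients that are discontinued will revert to their normal treatment plan, and continue in their respective clinics".

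Sections 5.4 and 5.5.5 place follow-up at day 7, day 14 and months 3, 6 and 12 after day 0. Section 5.8 says that all data are analysed by intention to treat. It gives no method for missing outcomes, and its only allowance for dropout is to raise 98 patients to 110 for an expected 10%. Section 5.5 refers to standard operating procedures and a manual of operations, which are not part of the document reviewed.

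**The concern.** An intention-to-treat comparison needs the outcome of everyone randomised, or a stated way of handling those whose outcome is unknown. The retention sentence covers participants who withdraw from treatment. Tenotomy is a single procedure on day 0, so a patient who later misses visits, or whom the investigator removes, has not obviously withdrawn from treatment. For such patients the plan describes an invited visit and a return to usual care, and nothing after that.

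These triggers may be related to the outcome. Patients who stop attending, or who are removed for health or compliance reasons, may differ in ulcer risk. The trial compares a procedure with offloading, so removal could also differ by arm. Procedure-related sepsis is the clearest case, since it would plausibly arise mainly in the tenotomy arm. Recruiting extra patients restores the number analysed but does not restore the comparison as randomised.

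**Working it through.** **1. The plan's own figures.** With the inputs of section 5.8 (difference 4, standard deviation 10, two-sided 5%, power 80%, ratio taken as 1), the formula gives 2 × [10 × (1.960 + 0.842)/4]² = 98.1, which matches 98. For dropout, 98/0.90 = 108.9, and the plan uses 110; 110 × 0.90 = 99, just above 98. The formula's result is the size of one arm, while the text uses it as a total. That is a separate matter, and 110 is taken here as the trial total, as written.

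**2. When the missed-visit rule can act.** Five scheduled visits follow day 0: day 7, day 14 and months 3, 6 and 12.

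| Run of three missed visits | Ends at | Time left to month 12 |
|---|---|---|
| day 7, day 14, month 3 | month 3 | about 9 months |
| day 14, month 3, month 6 | month 6 | about 6 months |
| month 3, month 6, month 12 | month 12 | none |

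Two of the three runs finish early. If the invited visit is not taken up, the unobserved time reaches back to the last visit attended. Missing all five visits already contains a run of three, so on this count the 5-visit rule adds no pattern. These are counts of patterns, not probabilities.

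**3. Scale of dropout against events.** Assume 55 per arm (the allocation ratio is not given as a number). Planned dropout is 0.10 × 110 = 11. Expected patients with an ulcer are 0.10 × 55 + 0.06 × 55 = 5.5 + 3.3 = 8.8.

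**4. Extreme bounds.** Suppose 5 control and 3 tenotomy patients are known to have an ulcer, and k outcomes per arm are unknown among 55 randomised. The control-minus-tenotomy difference lies between (5 − 3 − k)/55 and (5 + k − 3)/55.

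| k per arm | Lower bound (points) | Upper bound (points) |
|---|---|---|
| 1 | +1.8 | +5.5 |
| 2 | 0.0 | +7.3 |
| 3 | −1.8 | +9.1 |
| 6 | −7.3 | +14.5 |

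The lower bound reaches zero at k = 2 and is negative from k = 3.

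**5. A milder scenario.** Assume true rates of 10% and 6%, 10% of each arm unknown, and unknown patients in one arm only ulcerating at m times that arm's rate. The rate among known outcomes in that arm is (p − 0.1 × m × p)/0.9.

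- Control arm affected: 8.89% (m = 2) or 7.78% (m = 3), so the difference is 2.9 or 1.8 points.
- Tenotomy arm affected: 5.33% or 4.67%, so the difference is 4.7 or 5.3 points.

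The true difference is 4.0 points throughout.

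**6. Significance.** Two-sided Fisher tests on 55 per arm give p = 0.72 for 5 vs 3; 1.00 and 0.20 at the two k = 3 extremes (5 vs 6, 8 vs 3); and 0.39 and 0.042 at the two k = 6 extremes (5 vs 9, 11 vs 3).

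**The case against.** The strongest reply is that returning to a normal treatment plan describes care and does not say that data collection stops. The retention sentence sits in the same list and may have been meant for everyone, discontinuing patients are invited to a visit, and the operating procedures may provide for tracing. This stands in part. A reader might infer that the intention-to-treat analysis will lack these outcomes, and the document does not establish that. It leaves collection undescribed. But if the retention sentence was meant for everyone, it conflicts with the unqualified statement about discontinued patients, so a wording change is needed on either reading.

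A reader might also count day 0 as a visit that can be missed, which would add a run ending at day 14 with about 11.5 months left. The plan does not support that well: day 0 is when the allocated treatment is given and the point from which later follow-up is timed.

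Finally, the figures above describe dropout of any cause, not dropout due to these rules. Some patients who miss three visits in a row would be hard to follow under any rule. The bounds assume that every unknown patient ulcerates in one arm and none in the other, and the milder scenario always leaves a difference favouring tenotomy. All of this stands, so the figures serve only as a guide to scale.

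**Conclusion.** The point holds as a gap in the wording and in the analysis plan. For patients discontinued for missed visits, by the investigator, or for procedure-related sepsis, no outcome collection to 12 months is described, and there is no rule for missing outcomes to support the stated intention-to-treat analysis. Patients who withdraw from treatment are promised follow-up, but that promise is not reconciled with the general statement about discontinued patients.

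The size is unknown, because the document does not say what share of the 10% dropout these rules would cause. With 55 per arm assumed, planned dropout exceeds expected ulcer patients, and a few unknown outcomes per arm are enough for extreme bounds to include no effect or a reversal. What is mainly at risk is the estimate. It would go too far to say that the trial's significance depends on this: 5 vs 3 is already far from significant, and of the extremes tested only 11 vs 3 falls below 0.05. This is a cheap improvement worth making.

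**What to change.** **Section 5.2.** State that discontinuation for any of the listed reasons ends study visits or treatment but not outcome collection, and reword the sentence on discontinued patients so that it agrees with the retention sentence. Unless consent is withdrawn or the patient dies, obtain treated-foot ulcer status, and amputation status, to 12 months for every randomised patient. Sources can be a visit, a telephone call, or the electronic record already used for screening (section 10, Recruitment), subject to consent covering this. Collection of ulcer status should not stop at a listed endpoint that is not itself the primary outcome. One example is "Patient incurs minor or major amputation on either treated or nontreated limb", which includes the limb that was not treated.

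**Section 5.8.** Analyse all patients as randomised, with a prespecified sensitivity analysis for outcomes still unknown. Flag ulcers found without a photograph as not confirmed by the two external evaluators.

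**Cost.** Some protocol wording and a few calls or record look-ups; planned dropout of any cause is 11 patients. Ulcers identified this way are less firmly confirmed, and consent must cover look-up after discontinuation (the consent pages were not available for this review). No treatment or discontinuation rule needs to change.

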5.5 Detailed description of visits

The following section describes all visits in the study. All visits will be conducted by trained scientific staff, under responsibility of site investigator, and according to the delegation log. Procedures included in the visits will be conducted according to standard operating protocol (SOP) and manual of operations (MOP). It is the responsibility of principal investigator to train scientific staff in SOP and MOP. And to ensure that relevant SOP and MOP are available for the study personnel before procedures are performed.

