- Foot examination
 - Inspection of pressure point, and deformities
 - o Pulses
 - o Deformities
 - o New Ulcers

- Standard care & offloading
 - See section 5.3.2
- Tenotomy/conservative treatment application
 - The allocated treatment is performed
 - For details on tenotomy see section 5.3.1
 - For details on conservative treatment see section 5.3.2
- Impending ulcer evaluation
 - Anatomical placement
- Ulcer evaluation (if ulcer incurred)
 - Assessment of ulcer surroundings
 - Assessment of infection
 - Assessment of healing
- Measurement of longest length, width and depth in mm
- Measurement of area in mm³(length*width*depth)
 - Assessment of incision site (where applicable)
 - o Measurement of length, width and depth of ulcer(s) after debridement
- Categorizing by Texas Grading System
- Footwear assessment
 - Footwear and/or current offloading is evaluated
 - All patients in conservative and treatment group will be offered therapeutic sandals with customized insole at this visit
- Changes in medicine/new ailments
 - o Changes to the patient's medicine, and/or new diagnosis are registered

5.5.3 Visit Day 7, 14

The following is a specification of the above mentioned visits. If at any visit, before week 10, the impending ulcer has been deemed as progressed to active ulcer, patient is planned for end visit. If Patient incurs ulcer between visit day 14 and 3 month visit, patient contacts study personal to arrange end visit as soon as possible.

• Foot examination

- Inspection of pressure point, and deformities
- o Pulses
- o Deformities
- New Ulcers (not associated to registered impending ulcers)
- Changes in medicine/new ailments
 - o Changes to the patient's medicine, and/or new diagnosis are registered
- Standard care & offloading
 - See section 5.3.2
- Impending ulcer
 - Has impending ulcer progressed to active ulcer
- Ulcer evaluation (if relevant)
 - o Assessment of ulcer surroundings
 - o Assessment of infection
 - Assessment of healing
 - o Ulcer photo
 - o Measurement of longest length, width and depth in mm
 - Measurement of area in mm³(length*width*depth)
 - Assessment of incision site (where applicable)
 - o Measurement of length, width and depth of ulcer(s) after debridement
 - o Categorizing by Texas Grading System
- Footwear assessment
 - o Footwear and/or current offloading is evaluated
- Complications
 - Complications associated with tenotomy is registered (if relevant)
 - SAE is registered (if relevant)

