5.8 Statistics

All statistical analysis will be performed using the version of SAS currently used at our institute. All data will be analyzed on the intention to treat basis. All baseline data will be presented using appropriate summarizing statistics. Appropriate comparable statistical analysis will be applied to

- Incidence of new ulcer(s) in treated limb
- Mean time (in days) to healing of incision sites
- Incidence of minor amputations
- Incidence of major amputations

Odds-ratio will be applied to

- The incidence of secondary infection
- Pain in treated limb, associated with tenotomy
- Transfer lesion

Sample-size

The calculation is done with a Type 1 error rate (α) at 5%, and a power (1- β) at 80%. The primary endpoint is number of new ulcers incurred.

In the general diabetic population life time prevalence of diabetic ulcers has been reported at $15-25\%^{24}$, the yearly incidence in the same group is 6%. This study focuses on patients with a deformity reported to have a 1.5 hazard ratio²⁵, and signs of an impending ulcer like callus formation, which has been reported with a relative risk of 11^{26} . The incidence of new diabetic foot ulcers incurred by the study population is set at 10%, according to the above mentioned considerations.

The incidence in the intervention group (μ_A) is set at 6%, so the anticipated reduction in incidence is 4% compared to the incidence in the control group (μ_B) which as above mentioned is set at 10%. However, the numbers for incidence of new diabetic foot ulcers is an uncertain size, especially when looking at the specific group we are looking at, therefore the standard deviation (σ) is set at 10.

The calculator used is a 2 means, 2 sample, 2-sided equality calculator. The formula is

 $nB=(1+1/\kappa) ((\sigma z1-\alpha/2+z1-\beta)/(\mu A-\mu B))2$

nB= Sample size

 κ = The matching ratio

With the above described parameters, the sample size is 98 patients, which due to an expected dropout of 10% will be extended to 110 patients.

6. **Perspective**

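### Staff who can see the treatment decide which lesions go for ulcer confirmation, the evaluators are not stated to be masked, and no rule covers a call they reject

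*Combined protocol and SAP*

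**What the plan says.** - **Arms (section 5.3).** One arm receives needle tenotomy plus offloading, the other offloading alone. The available text does not mention masking of patients, site staff, evaluators or analyst.
- **Who assesses (section 5.5).** "All visits will be conducted by trained scientific staff". At the Day 7 and 14, follow-up and End visits (sections 5.5.3 to 5.5.5) these staff judge whether the impending ulcer has become active. The same checklists include the incision site, where there is one, and tenotomy complications.
- **What is judged.** Section 3 defines an impending ulcer by nail changes and heavy callus at the usual ulcer sites. No threshold separates this from an early ulcer.
- **Confirmation (section 5.2, Endpoints).** When a new ulcer occurs, "pictures will be send to two external evaluators to be confirmed as new ulcer". The section does not say what the evaluators know, how a disagreement is settled, or what follows a rejected call.
- **End visit.** Under section 5.5.3, if at a visit before week 10 "the impending ulcer has been deemed as progressed to active ulcer, patient is planned for end visit". Note 1 to the section 5.4 table ties the End visit to a named endpoint. Section 5.5.4 ties it to progression, or to reaching 12 months without progression.
- **After an ulcer (section 7.3).** Patients not allocated to tenotomy will be offered it if an ulcer occurs and the procedure is considered relevant. Section 5.2 lists relevant unplanned surgery as an endpoint in itself.

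**The concern.** The primary endpoint depends on where an assessor draws the line between a threatened and an actual ulcer, and the assessor can see which treatment was given. Knowledge of the arm can move that line without any intent.

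External confirmation is the main safeguard, but it has two gaps. It acts only on positive calls: pictures are sent when staff have called an ulcer, and the ulcer photograph belongs to an evaluation done only if relevant. A lesion that staff do not call need never be photographed, so under-calling in one arm cannot be detected. For the lesions that are sent, nothing says the evaluators are kept from knowing the arm.

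The handling of an unconfirmed call is also open. If the site's call leads to the End visit and the evaluators then reject it, the plan does not say whether that patient returns to the 3-, 6- and 12-month visits. A control patient might meanwhile have been offered tenotomy. If staff call ulcers at different rates by arm, this loss of observation would also differ by arm.

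**Working it through.** **Inputs from section 5.8.** The type 1 error is 5% and the power 80%. On the method, the section says: "The calculator used is a 2 means, 2 sample, 2-sided equality calculator". The control incidence is 10%, and the intervention incidence "is set at 6%, so the anticipated reduction in incidence is 4% compared to the incidence in the control group". The SD is 10. The stated size is 98, raised to 110 for 10% dropout. Section 5.6 gives blocks of 5 and no allocation ratio, so **1:1 is an assumption** below.

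**Step 1: reproduce the plan's figure.** With σ multiplying the sum of both normal quantiles and a ratio of 1:

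n = 2 × (10 × (1.960 + 0.842) / 4)² = 98.1, against 98 stated.

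Dropout: 98 / 0.90 = 108.9, close to the stated 110 (99 / 0.90 = 110). The formula returns a number per arm, while the plan uses 98 and 110 as totals. That is a separate matter; both readings are shown in step 2.

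**Step 2: the planned effect in patients with an ulcer.**

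| Patients per arm | Control, 10% | Intervention, 6% | Gap |
|---|---|---|---|
| 55 (110 in total) | 5.5 | 3.3 | 2.2 |
| 49 (98 in total) | 4.9 | 2.94 | 1.96 |
| 98, if per arm | 9.8 | 5.88 | 3.92 |
| 110, if per arm | 11.0 | 6.6 | 4.4 |

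At 55 per arm the expected total is 5.5 + 3.3 = 8.8 patients with an ulcer.

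**Step 3: effect of a few differential calls on the estimate.**
- Two net calls: 2/55 = 3.6 points; 2/49 = 4.1 points.
- Three net calls: 3/55 = 5.5 points; 3/49 = 6.1 points.
- The planned difference is 4 points.

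**Step 4: error rates that would produce the planned gap with no true effect.**
- True rate 6% in both arms: over-calling 0.04 / 0.94 = 4.3% of ulcer-free control patients.
- True rate 10% in both arms: missing 0.04 / 0.10 = 40% of intervention-arm ulcers, which at 55 per arm is 0.40 × 5.5 = 2.2 patients.

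**Step 5: significance.**
- Fisher's exact test gives p = 0.49 for 3 against 6 of 55, and p = 0.71 for 3 against 5 of 49.
- With 2 to 6 intervention events, 8 to 10 extra control events are needed for p < 0.05.
- The plan names no test for the primary endpoint. Under an assumed chi-square test at 55 per arm, a systematic bias of the planned size (10% against 6% recorded, no true difference) would raise the rejection probability from about 5% to about 11%.

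**Step 6: the End-visit passages side by side.**
- Section 5.2 places confirmation under the new-ulcer endpoint, and note 1 in section 5.4 ties the End visit to a named endpoint. Together they can mean that confirmation comes first.
- Section 5.5.3 plans the End visit on the staff's judgement and does not mention confirmation. It covers visits before week 10, and has patients who ulcerate between day 14 and month 3 contact the study for an End visit.
- Section 5.5.4 refers to progression, again without confirmation. Section 5.5.5 has no trigger sentence.
- None of these passages covers a call that is not confirmed.

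**The case against.** **Order of events.** A reader might infer that the plan prescribes call, End visit, then confirmation, so that every false call removes a patient. No passage states that order. Sections 5.2 and 5.4 can be read the other way, and the ulcer photograph is listed at Day 7, Day 14 and follow-up visits, so it could be sent before any End visit. This stands: the defect is silence about rejected calls, together with passages that do not agree on the trigger. Section 5.2 asks patients who withdraw from treatment to stay in follow-up, but a rejected ulcer call is a different event.

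**Detail held elsewhere.** Section 5.5 refers to operating procedures and a manual that are not available here, and the numbering goes from 5.6 to 5.8. A reader might infer that the evaluators will know the arm. The text supports only that masking is not stated. A rule protecting the primary endpoint still belongs in the protocol.

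**Structured assessment.** Lesions are measured and graded on the Texas system. This limits impressionistic calls but masks nobody, and it applies only once an ulcer is being evaluated.

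**Size.** An over-call must pass two external evaluators, and the arithmetic above takes no account of that. This stands for over-calls; under-calls meet no such check. Section 4 words the endpoint as a number of ulcers, whereas the working counts patients with an ulcer, in line with the stated incidences. The fragility also reflects how few events are expected, which is a separate sample-size issue.

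**Photographic clue.** Section 5.3.1 places the puncture on the plantar side near the web, made with a 1.2 mm needle. An early photograph might show it, but nothing indicates that a mark would remain visible over 12 months. It is a possibility only.

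**Conclusion.** The concern holds in this form: staff able to see the treatment make the first call on a judgement-based primary endpoint. Positive calls are confirmed by evaluators not stated to be masked, negative calls are not checked, and no rule keeps an unconfirmed patient in follow-up.

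Assuming 1:1 allocation of 110 and counting patients, the planned gap is 2.2 patients among 8.8 expected, so two or three net differential calls equal it. If 110 were per arm, it would be 4.4 patients.

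A reader might infer that a few biased calls could turn a null trial into a significant one. The figures do not support that: a gap of the planned size is far from significant, and 8 to 10 extra control events would be needed. What is exposed is the effect estimate, with a moderate rise in false-positive risk if the bias is systematic. That the trial is unmasked is itself inferred from the visibly different treatments and the absence of any masking text.

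**What to change.** 1. State that the two existing evaluators read coded photographs without knowledge of arm, visit or site. Cover puncture marks where this does not hide the lesion or the anatomy needed to judge it.
2. In both arms, photograph and send every suspected ulcer at a deformity-associated site on the treated foot under one written criterion. Exclude the tenotomy puncture, which exists in one arm only; a rule to send every skin break would build in a difference between arms.
3. Define the primary event as the ulcer confirmed by the evaluators, with a pre-stated rule for disagreement. Analyse staff-called ulcers as a sensitivity analysis.
4. Keep a patient whose call is not confirmed on the visit schedule to 12 months. Reconcile sections 5.2, 5.4, 5.5.3 and 5.5.4 on whether confirmation must precede the End visit, and make clear whether the ulcer referred to in section 7.3 is a called or a confirmed one.

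If the operating procedures already cover any of this, move the rule into the protocol.

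The cost is protocol wording, a coding step and a few more photographs, with no additional evaluators. Masking will be imperfect, because a straightened toe may still hint at the arm.
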